- c. *Patient assessments.* Patients will complete assessments at baseline and at 3 and 6 months post-intake. Brief baseline assessments will be conducted by research staff either in person at the participating centers or via phone. Multiple strategies will be used to prevent attrition. At baseline, multiple sources of contact information will be recorded for patients. Contact information will be updated by periodic phone calls. In addition, patients will provide detailed contact information of two friends or family members ("locators") who can be contacted if research staff is unable to reach them. Reminders will be made via phone, text, and email: the reminders will not contain any details about the study and will simply note a reminder about an upcoming appointment. Patients who cannot be reached over the phone for follow-up will be identified as needing follow-up from the designated outreach team, who will attempt in-person contact in at the patient's home or OUD center. Patients will receive a slightly escalating schedule of compensation in the form of a Clincard, a reloadable Mastercard card for completing the baseline (\$20), 3-month (\$20), and 6-month follow-up (\$25) assessments. Our analysis plan assumes 80% completion of patient follow-up assessments.

- d. *Electronic medical record (EMR)*. All 30 sites have agreed to document CM session delivery in their medical records (using the Post-Session Self-Report Form) and to extract patient data into an online Qualtrics template created for this project (using the Medical Record Data Extraction Form). Providers will enter session data into the Post-Session Self-Report Form in the medical record. Data will be extracted from the medical record from staff at the participating opioid treatment centers at two timepoints: a) end of 9-month Implementation phase and b) end of 12-month Sustainment phase.

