- e. *Audio recordings of CM sessions*. CM staff in both implementation conditions will be required to submit audio recordings of CM sessions once per month in order to receive performance feedback and P4P incentives. Submissions will be made using the Brown CIS recommended solution of Virtru encrypted email. A Brown research staff member will email each site a reminder that audio recordings are due using Virtru encrypted email: as long as providers reply to this email, audio recordings will be encrypted. Use of Virtru will be demonstrated during both the upfront didactic training and the ongoing monthly coaching calls.

9. Key Measures.

- a. *Implementation outcomes*. Our **Primary Aim** tests the effectiveness of the two implementation conditions (ATTC vs. E-ATTC) on CM Exposure, CM Competence, and CM Sustainment.
 - i. **CM Exposure**. This is a patient-level measure of the number of CM sessions delivered per patient during the 9-month Implementation phase. As described above, at each site, data will be extracted from the medical record (by center staff blind to condition) and entered into the Medical Record Data Extraction Form for the 25 patients enrolled in the study (25 patients * 30 sites = 750 patients) at the end of the Implementation phase. A Medical Record Data Extraction form will be filled out for every Self-Report Data Form completed in the patient medical record. Based on empirically derived benchmarks from prior RCTs,¹⁰ 10 or more complete CM sessions per patient (out of a maximum of 24) is the target level of CM Exposure to merit P4P incentives. To reach the target level of CM Exposure for a given patient, at least 10 Medical Record Data Extraction forms must be completed.
 - ii. **CM Competence**. This is a staff-level measure of staff's skill in CM delivery during the 9-month Implementation phase. Each month, CM staff will submit audio-recordings, one of which will be randomly selected for rating by coders blind to implementation condition using the CM Competence Scale¹² (CMCS). The scale contains 9 items scored from 1 to 7, with 7 denoting excellent competence. Based on empirically derived benchmarks from prior RCT research,¹³ an average CMCS score of 5.8 across items is the target to earn P4P incentives. A continuous measure of CMCS scores will be created for each staff on a monthly basis.

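### CM Competence is scored on a session the provider can choose, and the score pays a bonus in E-ATTC only; CM Exposure, also bonus-linked, has no second source

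*Combined protocol and SAP*

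**What the plan says.** **Competence.** Section 9.a.ii: "Each month, CM staff will submit audio-recordings, one of which will be randomly selected for rating by coders blind to implementation condition". Section 7.a (Performance feedback) adds that a session must come from the month in question and be sent by its last day. It provides for a random draw when a provider has sent more than one. No section says which of the month's sessions is to be recorded or sent. The number of recordings is put differently in different places:

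- Overview of Study Design: one a month.
- Section 6.b: a minimum of one in one sentence, one in another.
- Section 7.a: a minimum of one.
- Section 8.e: staff "will be required to submit audio recordings of CM sessions once per month".
- Section 9.a.ii: a plural from which one is drawn.

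Section 7.b pays E-ATTC providers $50 for each month in which the rated session averages at least 5.8 on the CMCS.

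**Exposure.** Section 8.d: "Providers will enter session data into the Post-Session Self-Report Form in the medical record". Section 9.a.i: "A Medical Record Data Extraction form will be filled out for every Self-Report Data Form completed in the patient medical record". The bonus threshold uses the same count: "To reach the target level of CM Exposure for a given patient, at least 10 Medical Record Data Extraction forms must be completed". Section 7.b pays $200 for each patient who reaches it, again in E-ATTC only. The Overview and Section 8.d require documentation in both arms.

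**Checks.** The only sensitivity analyses named (Section 10.a) concern multiple imputation. Section 9.b.i corroborates self-reported abstinence with urine screens; neither of these two implementation outcomes has a comparable second source.

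**The concern.** In both outcomes the quantity analysed is also the quantity paid for, and it is paid for in one arm only. For Competence, an E-ATTC provider has a financial reason to send a session that went well; an ATTC provider does not. The outcome is meant to describe the quality of CM during the Implementation phase. If selection is stronger in one arm, the comparison mixes skill with selection. For Exposure, the primary hypothesis is about sessions received, while the data count forms written. P4P is intended to raise real delivery, but the plan cannot tell more delivery from more complete paperwork. Two of the three primary outcomes are affected, in different ways and under different conditions.

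**Working it through.** **1. Where selection can enter for Competence.** The order of events is: a session is held, it is recorded, it is sent, a draw is made among those sent, and a coder rates it. The calendar-month rule limits the first step to a month. The draw acts at the fourth step and does nothing if one recording is sent, which every section permits. Blinding acts at the fifth. Nothing governs the second and third steps, so a provider who complies fully may still choose.

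**2. Illustrative size for Competence.** The documents give no within-provider SD. Taking a provider's session scores as independent normals, the expected best of k, in SD units, is the integral of x·k·φ(x)·Φ(x)^(k−1):

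| k | Expected best (SD) |
|---|---|
| 2 | 0.56 |
| 3 | 0.85 |
| 4 | 1.03 |

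This assumes perfect ranking, and only the difference between arms in selection would bias the comparison.

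**3. Exposure, conditional on unequal documentation.** A delivered session without a form counts as no session, not as missing, so imputation does not reach it. Spurious difference = delivered sessions × gap in form completeness. With assumed inputs: 6 × 0.05 = 0.3 and 10 × 0.15 = 1.5 sessions.

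Take 8 delivered sessions in both arms, SD 4-6, ICC 0.05-0.20, and 375 patients per arm divided by the design effect 1 + 24 × ICC (normal approximation):

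| Completeness, ATTC vs E-ATTC | False difference | Chance of p < 0.05 |
|---|---|---|
| 90% vs 95% | 8 × 0.05 = 0.4 | 7-15% |
| 80% vs 95% | 8 × 0.15 = 1.2 | 21-79% |

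**4. Size of the incentives.** In Section 7.b's own example, Exposure pays up to 10 × $200 = $2,000, and 2,000/45,000 = 4.4% of the stated mean salary. Competence pays up to 9 × $50 = $450, or 1.0%.

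**5. Precision of a patient-report check.** Section 8.c assumes 80% follow-up: 750 × 0.80 = 600, so 300 per arm and 20 per center. For the difference EMR count minus patient report, with assumed SD and ICC, SE = SD × √[(2/300)(1 + 19 × ICC)] and half-width = 2.048 × SE (t, 28 df).

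| SD | ICC | SE | 95% half-width | Power for a 1-session gap |
|---|---|---|---|---|
| 2 | 0.01 | 0.178 | 0.36 | above 99% |
| 4 | 0.05 | 0.456 | 0.93 | 56% |
| 4 | 0.20 | 0.716 | 1.47 | 27% |

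If both interviews are needed and losses are independent (750 × 0.64 = 480; 240 per arm, 16 per center), the half-widths are 0.40, 0.99 and 1.50.

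**The case against.** The plan has real safeguards. Documentation, recording and feedback apply in both arms, coders are blind, sessions must come from the current month, and a draw is made when several are sent. The differing recording counts can be read as loose wording around one operative rule in Section 7.a. The Competence bonus is at most 1.0% of salary, below the 4 to 7% range that Section 7.b cites as enough to change performance. It is also a step at 5.8: a provider needs a passing session, not the best one, so an expected maximum fits the incentive poorly. The Exposure bonus is a step too, at 10 sessions, and a uniform completeness gap ignores that.

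Most of this stands as a limit on size. It does not remove the Competence problem, because a provider who sends one chosen recording is within Section 7.a on any reading.

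Two stronger readings go too far.

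- A reader might infer that Exposure is biased even if the plan is followed exactly. It is not: providers in both arms are to record their CM delivery, and all 30 sites agreed to document it. With full documentation in both arms there is no completeness gap.
- A reader might infer that providers choose the best of a full month's caseload. The documents do not support this. They do not say that every session is recorded, and the Overview has one recorded per month.

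CM Sustainment offers only a partial check. E-ATTC activities have stopped by then, but it uses the same form count, and a smaller effect could mean less real delivery.

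**Conclusion.** The Competence point holds under exact compliance: the rated session is not fixed independently of the provider, and the incentive to choose differs by arm. The likely direction favours E-ATTC. The size is unknown, and 0.56-1.03 SD is an illustration under perfect ranking among 2-4 sessions, not an estimate or a bound.

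The Exposure point is secondary and conditional. It needs documentation to fall short unequally; if it did, assumed gaps of 5-15 points would shift the mean by 0.3-1.5 sessions. What holds without assumptions is that no second source is planned that could show it.

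Nothing in the documents shows that either bias will occur. The change should be made, because it is inexpensive and two primary outcomes are involved.

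**What to change.** **1. Competence (the main change).** Replace the selection text in Sections 7.a and 9.a.ii with one rule for both arms that fixes the rated session independently of the provider. For example, draw a date at random for each provider-month and name it in the monthly reminder email already planned in Section 8.e. The next CM session on or after that date is the one rated. Draw the date early enough to leave eligible sessions in the calendar month. Make the Overview and Sections 6.b, 7.a, 8.e and 9.a.ii agree on the number of recordings. Report compliance and missing provider-months by arm, with a sensitivity analysis that lets missing months score lower in one arm.

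The cost is a random date per provider-month, less scheduling freedom and some missing months. At an assumed 10%, these are 54-135 of 540-1,350 provider-months (60 × 9 to 150 × 9). An announced date leaves some room to prepare.

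**2. Exposure.** In both arms, add one question to the 3- and 6-month interviews: how many CM sessions were attended, whether or not a prize was drawn. Compare the answer with EMR sessions dated up to the interview, which requires a session date in the extracted data. Pre-specify the EMR-minus-report difference by arm with a cluster-adjusted 95% CI, and a sensitivity analysis of CM Exposure using patient report. State that recall error and loss to follow-up limit it, that it can detect only a large gap, and that a null result is not reassurance. The cost is one question at two visits already planned and two analyses.

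**3. Separate wording points.** Section 9.a.i says "data will be extracted from the medical record (by center staff blind to condition) and entered into the Medical Record Data Extraction Form". Whole centers are randomized, so delete the blinding claim or say how it is kept. Section 8.d extracts data "at two timepoints: a) end of 9-month Implementation phase and b) end of 12-month Sustainment phase", while Section 7 needs exposure counts for monthly feedback and bonus confirmation; state where those counts come from.

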one of three trained CM staff will turnover during the project's first two phases, each center will be required to identify one or more replacement CM staff. Thus, if one of the initially trained CM staff withdraws from the study for any reason during the Preparation or Implementation phase, a replacement CM staff will be immediately trained.

- c. *Community-based OUD treatment center patients (Patients).* Each center will agree to deliver CM to all patients newly admitted over a 6-month period. In addition, each center will be asked to enroll approximately one eligible CM patient per week to complete research assessment measures. Eligible patients will be: a) adult patients, b) newly admitted to the opioid treatment center within the past 30 days, and c) prescribed any FDA-approved OUD medication. To optimize ecological validity, exclusion criteria will be minimal and will only include issues that could interfere with the ability to complete a brief intake interview including acute intoxication, acute psychosis, acute mania, or cognitive impairment (prohibiting comprehension of the consent process), as reported by opioid treatment center staff or observed by research staff. We focus on newly admitted patients as opposed to those established in treatment because the need is highest among these patients: drop-out rates and missed doses are higher during the first 6 months of treatment (i.e., the "induction phase") than any subsequent period.

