- 5. **CM Procedures.** CM is a behavioral treatment in which providers deliver motivational incentives to patients for attaining specific treatment benchmarks. CM protocols have demonstrated effectiveness across various *reinforcement schedules* (immediate vs. delayed), *delivery schedules* (biweekly vs. weekly), and *behavioral targets* (abstinence vs. compliance).^{1,2} We will train staff from participating organizations in how to deliver a flexible, evidence-based CM protocol, which **targets compliance with opioid treatment** and **provides immediate reinforcement using escalating prize draws**. This protocol is supported by a robust literature that has shown: a) immediate reinforcement is associated with larger effect sizes than delayed;³ b) more frequent reinforcement is linked to better patient outcomes than less frequent or intermittent reinforcement;² and c) prize draws are less expensive, yet as effective (more cost effective) as vouchers.⁵ In addition, we completed pilot data collection with 12 opioid treatment centers as part of a NIDA funded pilot study (P20 GM125507) and centers indicated that they preferred to incentivize treatment compliance over abstinence or attendance at sessions.

The minimum goal will be for participating organizations to provide reinforcement in the form of a prize draw to patients at least once per week. Staff in the organizations will be responsible for monitoring patient compliance (defined further below) as part of the CM protocol.

For this study, we will train staff from participating OUD centers in a flexible CM protocol adapted from an evidence-based CM protocol initially created by [name], an international expert in CM delivery. Leadership of all participating organizations will define opioid treatment compliance as follows: Compliance rate = number of completed clinical

contacts per week / number of expected clinical contacts per week. Clinical contacts can be broadly defined as including medication doses, counseling sessions, and urine screens. Organizations will be allowed to determine the minimal compliance benchmark, and the weighting of clinical contacts to fit their organizational needs and preferences. In both conditions, organizations will be required to develop a clear CM compliance benchmark for earning prizes and a clear equation for how compliance would be calculated.

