In other weeks, patients at Organization B might have 3 clinical contacts expected (e.g., 1 medication dose, 1 urine screen, 1 counseling session). In these weeks, a patient who presented for only buprenorphine would have the following compliance rate: 1 actual visit / 3 expected visits = 33%, and would not receive a prize draw. Likewise, a patient that presented for only buprenorphine and a counseling session but missed the urine screen would have the following rate: 2 actual visits / 3 expected visits = 66%, and would not receive a draw. Patients would have to attend all 3 clinical contacts to receive a prize draw.

[figure not shown]
The CM protocol that staff will be trained in will consist of the following actions: 1) Review patient compliance for the week with patient using the organization definition of number of expected clinical contacts; 2) Clearly inform the patient if their compliance for week exceeded the organizational CM benchmark; 3) Clearly state the number of prize draws (if any) earned in the current session; 4) Administer CM prize draws as appropriate; 5) State number of draws patient can earn at the next session (goal-setting); 6) Praise patient's efforts towards compliance (even if the compliance benchmark was not met); and 7) Communicate confidence that patient's efforts will yield success in the future.

The evidence-based CM protocol⁶⁻⁸ that staff will be trained in will provide patients with increasing opportunities for winning cost-neutral (i.e., praise), \$1, \$20, and \$100 prizes for each week during which the CM compliance benchmark was attained. Draws increase by one for each week that compliance was attained. Failure to attain the benchmark or failure to attend the prize draw session resets draws for the next week down to one, with draws again escalating for sustained compliance. Patients will receive prize draws for up to 12 weeks, which is the median duration of the induction phase at participating centers (range

from 4 to 26 weeks). This progression will yield a maximum of 78 draws ($1+2+3+\dots+12$). Fishbowls will contain 500 slips; 250 state “good job!” but are not associated with a prize, 209 state “small,” 40 state “large,” and one “jumbo.” Using these probabilities and magnitudes of \$1, \$20, and \$100 for the three respective prize sizes, each draw has an average cost of \$2. Thus, for a 12-week protocol, each patient could earn 78 draws \times \$2/draw = \$156 in prizes.

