 - iii. **CM Sustainment**. This is a patient-level measure of the number of CM sessions delivered per patient during the 12-month Sustainment phase. Using the same protocol as for CM Exposure, data will be extracted at the end of the Sustainment phase from 25 randomly selected patients meeting eligibility criteria (i.e., newly admitted to OUD pharmacotherapy during the Sustainment phase; 25 patients * 30 sites = 750 patients). A continuous measure of the number of sessions received, as counted by the number of Medical Record Data Extraction forms completed, will be created for each patient.

b. *Patient outcomes.* Our **Secondary Aim** tests the effectiveness of the two implementation conditions (ATTC vs. E-ATTC) on two patient outcomes: Opioid Abstinence and Opioid-Related Problems.

- i. **Opioid Abstinence.** Patient abstinence from opioids will be assessed via 3- and 6-month post-baseline interviews, during which patients will self-report days of abstinence using the Timeline Followback (TLFB).²⁰ Abstinence will be corroborated via dip urine screens from Redwood Toxicology testing for: heroin/opiates, oxycontin, benzodiazepines, cocaine, methamphetamines, and THC. In addition, at the request of participating centers, single-panel screens will test for fentanyl, a highly lethal opioid not detected in multi-panel screens. A urine screen negative for all opioids (heroin/opiates, oxycontin, fentanyl) will be required for coding of 90 days abstinence. Other drug use detected via the TLFB or urine will be examined as covariates in the analysis.
- ii. **Opioid-Related Problems.** Opioid-related problems will be assessed via patient self-report at 3- and 6-months post-baseline using the Substance Problem Index,²¹ which is a count of DSM symptoms experienced by the patient (range from 0 to 11). Both Drs. [name] and [name] have successfully used this index²²⁻²⁴ in prior studies. The index will be tailored to focus specifically on problems due to opioids.

c. *Putative mediators.* Our **Exploratory Aim** tests putative mediators of implementation outcomes: implementation climate and leadership engagement. Organization-level scoring is described in **Analytic Plan**. The putative mediator scales are measured at the start of the Preparation phase and the midpoint of the Implementation phase.

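### CM Sustainment is a raw session count to phase end for patients admitted at any time in the 12 months, with no allowance for available time: a modest dilution, and a bias only if admission timing differs by arm

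*Combined protocol and SAP*

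**What the plan says.** Section 9.a.iii (CM Sustainment) samples, at each center, "25 randomly selected patients meeting eligibility criteria (i.e., newly admitted to OUD pharmacotherapy during the Sustainment phase". The score is "A continuous measure of the number of sessions received, as counted by the number of Medical Record Data Extraction forms completed". Section 8.d puts the second extraction at the "end of 12-month Sustainment phase", so sessions after that date are not seen. CM Sustainment is one of the three outcomes in the Primary Hypothesis (section 2.A).

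Three other places bear on how much time a sampled patient has.

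- **Course length.** Section 5 says "Patients will receive prize draws for up to 12 weeks". Section 9.a.i gives the P4P target as "10 or more complete CM sessions per patient (out of a maximum of 24". One session a week would make 24 sessions a 24-week course; two a week would make it 12 weeks. Section 5 sets only a minimum frequency, reinforcement "in the form of a prize draw to patients at least once per week". The documents do not say which reading applies.
- **Admission window.** Section 9.a.iii opens its sampling rule with "Using the same protocol as for CM Exposure". Section 3.c says "Each center will agree to deliver CM to all patients newly admitted over a 6-month period". The definition of eligibility in 9.a.iii nevertheless names the whole phase.
- **Model.** Section 10.b plans multilevel models with Cohen's d. Its covariates at organization, staff and patient level are given as examples, and none is admission date or available time.

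**The concern.** A patient admitted in the last fortnight of the phase can be drawn and scored on the same scale as one who had a full course. The count is exact for sessions inside the phase, but it mixes delivery with calendar opportunity.

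Two things are at stake. First, shortened windows pull both arm means down and add variation unrelated to delivery, so the absolute difference and Cohen's d shrink. Second, the comparison is fair only if patients in the two arms are admitted at similar times within the phase. The plan neither checks nor adjusts for this.

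**Working it through.** **Inputs from the documents.** Phase length 52 weeks (12 months; sections 6.c and 9.a.iii); extraction at phase end (8.d); course length L = 12 weeks (section 5), or 24 weeks on one reading of 9.a.i; 25 patients at each of 30 sites.

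**Assumptions.** Section 4.c gives only an average flow of 17 new patients a month, so the admission pattern is assumed: even in the base case, and a threefold linear fall or rise as the range. The documents give no delivery rate, SD, intraclass correlation or effect size for this outcome.

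**1. The plan's own figure.** 25 × 30 = 750, as stated. There is no power calculation to reproduce.

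**2. Share shortened and opportunity lost.** With even admissions, the share with less than a full course is L/52. Those patients lose half a course on average, so mean opportunity lost is L/104.

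For uneven admissions, let u be weeks from admission to phase end. The density is f(u) = (3 − 2u/52)/104 for a threefold rise and (1 + 2u/52)/104 for a threefold fall. The share is the integral of f(u) from 0 to L; the loss is the integral of (1 − u/L) f(u). For L = 12 and rising admissions: share (36 − 144/52)/104 = 0.320; loss (18 − 48/52)/104 = 0.164.

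| Course | Admissions | Shortened | Opportunity lost |
|---|---|---|---|
| 12 weeks | even | 23.1% | 11.5% |
| 12 weeks | falling / rising threefold | 14.2% / 32.0% | 6.7% / 16.4% |
| 24 weeks | even | 46.2% | 23.1% |
| 24 weeks | falling / rising threefold | 33.7% / 58.6% | 15.1% / 31.1% |

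Counting whole weekly sessions for the 12-week, even case gives 21.2% and 10.6% if the first session falls in the admission week, and 23.1% and 12.5% if it falls a week later.

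**3. If the 6-month window applies and opens the phase.** The last admission has 52 − 26 = 26 weeks, more than either course length. Both figures are then zero.

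**4. Cohen's d.** Let W be the available fraction of a 12-week course. E[W] = 1 − 0.231/2 = 0.885, E[W²] = 0.769 + 0.231/3 = 0.846, and Var(W) = 0.846 − 0.885² = 0.064. If sessions scale with W, d is multiplied by E[W]/√(E[W²] + Var(W)/CV²), where CV is the coefficient of variation of full-course sessions. This gives 0.84 for CV 0.5, 0.93 for CV 1 and 0.95 for CV 2: a fall of 16%, 7% or 5%. The fall in d is therefore not itself 11.5%; it depends on an SD the documents do not give.

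**5. Simulation.** Settings: 30 centers × 25 patients, one possible session a week, logit SDs 0.6 (center) and 1.0 (patient), arm log-odds 0.55, and a t-test on center means as a simplification of the planned model. The comparator is a hypothetical full-course count that includes sessions after phase end.

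- 12 weeks, base case: difference 1.28 falls to 1.14 sessions, d 0.41 to 0.36, power 61.6% to 59.7%; the ratio of means is 1.26 both ways.
- 12 weeks, nine settings in which the arms do not decline differently: difference 4% to 15% smaller, power 1.3 to 3.1 points lower.
- 24 weeks, four settings: difference 17% to 22% smaller, power 2.8 to 6.4 points lower.
- No true effect, similar timing: rejection 4.2% to 5.4%.
- Sessions per available week, 12 weeks: base difference back to 1.28, d 0.39, power 60.7%; gains of 0.4 to 2.0 points over the nine settings.

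**6. Unequal timing.** Take an extreme case in which ATTC admissions are even and E-ATTC admissions rise threefold. Opportunity then differs by 16.4 − 11.5 = 4.9 percentage points against E-ATTC. With no true effect, the raw count shows a difference of −0.22 sessions and 7.0% rejection; sessions per available week shows 0.00 and 4.7%. With a true effect (log-odds 0.55), power is 39.6% against 60.3%.

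**The case against.** **The window may already be limited.** The reference to the CM Exposure protocol could import the 6-month window, and if that opens the phase nothing is shortened. This stands as an ambiguity. The explicit definition in 9.a.iii names the whole phase, so the text as written favors the wider window.

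**The outcome is valid as defined.** It counts sessions inside the phase, and does so exactly. The dilution is measured against a different target, full-course delivery. The covariates in 10.b are only examples, so an available-time term is not ruled out. All of this is fair: the term is absent, not excluded.

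**The effect is small, and the larger cases are assumed.** This also stands. The adjustment gains about one point of power in the base case. The unequal-timing case is extreme. Its only textual support is that increasing patient flow is among the financing options coached in E-ATTC (section 7.b), and section 6.c ends that support before this phase.

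**The correction is incomplete if CM starts late.** With an assumed start lag of 0 to 4 weeks, the full-course difference is 1.28, the planned count 1.10 and the per-week version 1.16. That recovers (1.16 − 1.10)/(1.28 − 1.10), about a third of the loss. This belongs among the stated limits of the fix.

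**A stronger inference a reader might draw.** Because CM Exposure patients have a 6-month window in a 9-month phase, one could argue that Sustainment would look lower than Exposure even with identical delivery. Section 10.b plans no comparison of the two means; it tests condition on each outcome. The point affects no stated analysis.

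**Conclusion.** The concern holds at modest size. As written, 9.a.iii builds unequal observation time into a primary-aim outcome. On even admissions and a 12-week course, 23% of patients have a shortened window and opportunity falls by about 11.5%. The figures become 46% and 23% on the 24-week reading, and zero if an opening 6-month window was intended.

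A reader might infer that the shortened windows favor one arm or raise the false-positive rate. The documents do not support that: the rule is the same in both arms, and with similar admission timing the test is unbiased. The ratio of means is also unchanged as long as stopping is alike in the arms. What is lost is some of the absolute difference, some of Cohen's d, and roughly 1 to 3 points of power for a 12-week course. The power figures rest on assumed delivery rates, SDs and effect sizes and on a simplified test. Bias arises only if admission timing differs by arm, which the documents neither show nor exclude. This is a cheap improvement to consider; it does not invalidate the outcome.

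**What to change.** 1. Reconcile section 5 (12 weeks of draws) with section 9.a.i (maximum of 24 sessions), and state whether the 6-month window in 3.c applies in the Sustainment phase. If it does and opens the phase, nothing more is needed.
2. If whole-phase admissions are kept, record each sampled patient's admission date. Derive available weeks = min(course length, weeks from admission to phase end), rounding part-weeks up.
3. Account for available weeks in the planned multilevel model, either by analyzing sessions per available week or by prespecifying available weeks as a covariate on the count. Report the raw count beside it.
4. Use an admission cut-off only as a sensitivity analysis. It discards late admissions, where the arms may differ most once support has ended. In two simulated settings where only ATTC delivery fell by half, a cut-off lowered power from 95.0% to 91.5% and from 76.9% to 67.8%; sessions per available week raised it to 97.5% and 84.7%.

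**Cost.** One date, already needed to establish eligibility, and one derived variable; no extra patients and no later extraction.

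**Limits to state.** The rate assumes a roughly constant session rate and CM starting at admission. A start lag makes the correction partial. With 10% of patients stopping each week, the rate scaled to a full course is 7% too high for 12 weeks and 29% too high for 24 (3% and 12% if weighted by available weeks), so it should be reported as a weekly rate. Under the covariate option, the arm difference in sessions may itself grow with available weeks. How the moderation step in 10.b treats that should be settled in advance.
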